6.2.4 Safety Follow Up Period

After the last dose of the IMP, subjects will be required to enter a 30-day Safety Follow Up Period.

Subjects who complete an ED Visit are also required to complete the 30-day Safety Follow Up Period.

Subjects will be contacted 30 days (± 2 days) after the ED Visit to review adverse events and concomitant medications. Ongoing AEs will be followed as outlined in Section 7.4. Subjects will then be contacted for Vital Status every 24 weeks after the Safety Follow Up Visit by telephone until study completion.

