Elective hospitalizations to administer, or to simplify study intervention or procedures are not considered SAEs. However, all events leading to unplanned hospitalizations or unplanned prolongation of an elective hospitalization (i.e., undesirable effects of any administered treatment) must be documented and reported as SAEs.

Events Not to Be Considered as AEs/SAEs

Medical conditions present at the initial study visit that do not worsen in severity or frequency during the study are defined as Baseline Medical Conditions and should be reported in medical history and are not to be considered AEs.

Situations where an untoward medical occurrence has not occurred (e.g., hospitalization for elective surgery, social and/or convenience admissions) are not to be considered as AEs.

7.2 Time Period and Frequency for Collecting Adverse Event and Serious Adverse Event Information

The AE reporting period for safety surveillance begins when the subject is initially included in the study (date of first signature of informed consent/date of first signature of first informed consent) and continues until the last Safety FU per [Table 1](#).

- After informed consent, but prior to initiation of study drug, all SAEs, but only those non-serious AEs related to protocol-mandated procedures should be collected. All AEs that are not related to study procedures should be recorded as worsening medical history.
- Following initiation of study medication, all AEs should be collected, regardless of cause or relationship.
- Events will be summarized on the basis of the date of onset for the event.

A treatment-emergent AE will be defined as any AE that begins on or after the date and time of first dose of study drug through 30 days after last dose of study drug.

Serious Adverse Events

All SAEs, regardless of cause or relationship, that occur after the subject first consents to participate in the study (i.e., signs the informed consent) and throughout the duration of the study, including the protocol-required post treatment follow-up period, must be reported in the eCRF database and to the CRO as instructed. This also includes any SAEs resulting from protocol-associated procedures performed from screening onwards.

Any SAEs and deaths that occur after the post treatment follow-up visit but within 30 days of the last dose of study drug, regardless of causality, should also be reported. Any SAE assessed as

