8.6 Safety Analysis

Safety analyses will be conducted using the safety analysis set. The baseline will be defined as prior to the first AV-101 treatment. For Groups 1 and 2, the parent AV-101-002 study baseline will be used. For Groups 3 and 4, the AV-101-003 study baseline will be used and the placebo treatment data from the parent study will not be used. For the analyses of safety parameters, all four groups will be displayed individually. In addition, Groups 1 and 4 will be pooled as the optimal dose treatment group. Groups 2 and 3 will be pooled since they start with the non-optimal dose and then are switched to the optimal dose. An overall pool of all 4 groups will also be presented.

As previously defined, Groups 2 and 3 are treated with the non-optimal dose first and then are converted to the optimal dose. They will be further analyzed based on two treatment intervals. The first interval will start with the first day and end with the last day of the non-optimal AV-101 treatment. The second interval will start with the first day of the optimal AV-101 treatment, and end with the last day of the optimal AV-101 treatment or the data cutoff date for the analysis.

Treatment-emergent AEs (TEAEs), i.e. AEs that start or worsen at the start of AV-101 will be tabulated by system organ class and preferred term. Tables of fatal adverse events, SAEs, treatment-related AEs, and adverse events leading to withdrawal from investigation product will be provided. Subjects who experience more than one event in a given System Organ Class (SOC) and preferred term (PT) will be counted once within that SOC and PT. The total number of events and the number and percentage of subjects with each unique event will be reported.

The latest version of MedDRA will be used to code adverse events and the NCI CTCAE version 5.0 will be used to grade the severity of adverse events and laboratory toxicities.

Tabulations and detailed listings of subjects that experience AEs, AESIs, TEAEs, SAEs and ADEs and unexpected issues with inhaler use will be provided. AE severity and the relationship to AV-101 or the inhaler will also be reported.

For repeated safety events of special interest, incidence density will be compared between treatment arms by fitting a negative binomial model to counts of safety events with total weeks of study participation as an offset variable.

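### Sections 7.2 and 8.6 define treatment-emergent AEs differently, and the Group 2–3 interval analysis leaves onsets shortly after stopping, or in a gap at the switch, in neither interval

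*Combined protocol and SAP*

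**What the plan says.** Section 7.2 defines a treatment-emergent AE as one that "begins on or after the date and time of first dose of study drug through 30 days after last dose of study drug". It also fixes how events are placed in time: "Events will be summarized on the basis of the date of onset for the event".

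Section 8.6 describes TEAEs as "AEs that start or worsen at the start of AV-101". It does not refer back to 7.2.

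For Groups 2 and 3, which start AV-101 on a non-optimal dose and later move to the optimal dose, Section 8.6 adds: "They will be further analyzed based on two treatment intervals". On the first: "The first interval will start with the first day and end with the last day of the non-optimal AV-101 treatment". The second starts on the first day of optimal dosing and is to "end with the last day of the optimal AV-101 treatment or the data cutoff date for the analysis".

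Collection goes on after dosing stops. Section 6.2.4 states: "After the last dose of the IMP, subjects will be required to enter a 30-day Safety Follow Up Period".

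The other safety displays are not tied to these intervals: "For the analyses of safety parameters, all four groups will be displayed individually". Section 8.6 also plans pools (Groups 1+4, Groups 2+3, all four), tables of fatal events and SAEs, and listings.

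**The concern.** The two TEAE definitions differ in three ways:

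- **Worsening.** 8.6 includes it; 7.2 speaks only of AEs that begin.
- **End of window.** 7.2 closes it 30 days after the last dose; 8.6 gives no end.
- **Anchor.** 7.2 counts from study drug; 8.6 counts from AV-101. Section 8.6 takes baseline from the parent study for Groups 1 and 2 and from the LTE for Groups 3 and 4. The first AV-101 dose therefore precedes LTE entry in Groups 1 and 2, and 7.2 does not say which first dose it means.

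The intervals raise a separate problem. Each ends on a dosing day with no tail, yet events are placed by onset date. An event that is collected, and is treatment-emergent under 7.2, can have no interval to go into.

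Long-term safety is the objective of the study, and reporting before and after the optimal dose is a planned display. As written, event totals in the Group 2–3 interval tables need not reconcile with the same groups' overall TEAE tables under 7.2. Two programmers could also produce different tables from the same text.

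**Working it through.** The plan states no figure to reproduce. The check classifies test onset days under both rules.

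**Rules applied**

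- 7.2 window: first dose ≤ onset ≤ last dose + 30 days.
- 8.6 interval 1: first to last day of the non-optimal dose.
- 8.6 interval 2: first to last day of the optimal dose, with cutoff applying to subjects still on treatment.

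**Test subjects** (the day numbers are assumptions)

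| Dosing pattern | Onset day | TEAE under 7.2 | 8.6 interval |
|---|---|---|---|
| Non-optimal 1–200, optimal 201–400 | 150, 200 | yes | 1 |
| same | 201, 215, 400 | yes | 2 |
| same | 401, 415, 430 | yes | none |
| same | 431 | no | none |
| Non-optimal 1–200, stops without switching | 201, 230 | yes | none |
| Non-optimal 1–200, optimal 211–400 | 205 | yes | none |

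The mismatch arises after the final dose and in a gap at the switch. It does not arise after a direct switch: day 215 is within 30 days of the last non-optimal dose but falls in interval 2.

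**Data cutoff.** The second interval ends on the last dosing day or at cutoff, without saying which applies to whom. The natural reading is that cutoff serves subjects still on drug. If it applied to everyone, subjects who received the optimal dose would keep the final tail. The two readings give different tables. No cutoff rule is stated for interval 1.

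**The missing end of window in 8.6.** The Safety Follow-Up contact is 30 ± 2 days after the Early Discontinuation Visit, which may be up to 14 days after stopping. AEs can thus be collected up to 14 + 32 = 46 days after the last dose. Onsets on days 31–46 are outside 7.2 but not excluded by 8.6.

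**Share of the window in the tail.** With D days on the optimal dose, the tail is 30/(D + 30). The durations are assumed:

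- 12 weeks: 30/(84 + 30) = 26.3%
- 24 weeks: 30/(168 + 30) = 15.2%
- 52 weeks: 30/(364 + 30) = 7.6%
- 96 weeks: 30/(672 + 30) = 4.3%

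A Group 2 subject also has 24 weeks (168 days) of non-optimal dosing from the completed parent study. Counting at least that time:

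- 24 weeks on optimal: at most 30/(168 + 168 + 30) = 8.2%
- 52 weeks on optimal: at most 30/(168 + 364 + 30) = 5.3%

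These are shares of time for a subject who stops before cutoff, not shares of events.

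**The case against.** The strongest reply is that this is a wording gap in a supplementary display. Section 7.2 supplies the working window, and 8.6 is silent on its end rather than contradicting it. Worsening is largely handled at collection, because Sections 6.3 and 6.5.1 have worsening symptoms, and clinically significant new or worsening findings, recorded as AEs. Closing an interval on the last dosing day is a recognisable on-treatment convention. The plan keeps subjects on their dose until transition, so a gap is an exception. Section 8 calls itself an overview and leaves detail to a SAP.

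Much of this limits the point without removing it. The dosing-day convention would be acceptable if it were stated and the remaining events assigned somewhere, but no text does that. Stopping early and gaps are also foreseeable. Section 5.5 lets the investigator decide whether a down-titrated subject transitions, and Sections 6.7.1 and 7.7 provide for interruptions that could span the switch. A SAP cannot follow two definitions at once.

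Four stronger readings are tempting, and the documents do not support them:

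- **A reader might infer that deaths and SAEs after stopping vanish from the safety report.** They do not. Group, pooled, fatal-event and SAE tables and the listings are not interval-bound, and collection runs through follow-up. Only the assignment to an interval fails.
- **A reader might infer that Groups 1 and 4 follow 7.2 while Groups 2 and 3 do not.** The TEAE sentence in 8.6 covers all groups.
- **A reader might expect subject counts to add across intervals once this is fixed.** They would not. Each subject counts once per preferred term in a table, so the same term in both intervals counts twice across intervals and once overall. Only event totals can reconcile.
- **A reader might suppose that events cluster after stopping, or that serious events are lost disproportionately.** The documents give no AE rates, so neither can be shown.

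**Conclusion.** The point holds within these limits. Protocol Sections 7.2 and 8.6 carry two TEAE definitions that differ on worsening, end of window and anchor. On the natural reading of the cutoff wording, the Group 2–3 intervals exclude onsets in the 30 days after stopping and in any gap at the switch, although 7.2 counts them.

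For the intervals, the effect is confined to the Group 2–3 interval tables and to subjects who stop before cutoff or have a gap. The tail is about 15% of the optimal-dose window after an assumed 24 weeks and 8% after 52 weeks, and smaller when non-optimal time is added. How many events this moves cannot be computed. The conclusion assumes that subjects who stop before switching are still analysed in Group 2 or 3, and that no SAP text outside the supplied documents settles the matter.

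**What to change.** 1. Use one TEAE definition in 7.2 and 8.6: an AE that starts or worsens on or after the first AV-101 dose, through 30 days after the last AV-101 dose. State that the first dose is in the parent study for Groups 1 and 2 and in the LTE for Groups 3 and 4.
2. Assign events to intervals by onset date:
   - Interval 1 ends at the earliest of the day before the first optimal dose, 30 days after the last non-optimal dose, or data cutoff.
   - Interval 2 ends at the earlier of 30 days after the last optimal dose or data cutoff.
3. If a gap exceeds 30 days, onsets later in the gap still fall outside both intervals, although they precede the last AV-101 dose. Say so, and show them on a separate line so that event totals reconcile.

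For the test subjects, onsets on days 401–430 move to interval 2. Days 201–230 (no switch) and day 205 (gap) move to interval 1. Day 215 after a direct switch stays in interval 2.

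The cost is a wording change to protocol Sections 7.2 and 8.6, carried into the SAP. As protocol text it goes through an amendment with IRB/IEC approval under Section 9.3. Data collection does not change.

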2.1 Study Objectives

The objective of the study is to establish the long-term safety and tolerability of AV-101. The long-term effects on survival as well as clinical and quality of life measures over time will also be assessed.

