5.5 Down Titration

If a subject down titrated the dose of AV-101 in Study AV-101-002 and successfully completed 24 weeks of treatment, the subject should begin the LTE study with 2 capsules BID at the assigned dose i.e., either re-randomized if coming from placebo or continuing on the randomized dose but at two capsules BID if on active. If the subject does not tolerate the 2 capsules, they may down titrate to one capsule in the LTE. At the time of optimal dose selection and the transition to the optimal dose in subjects who have down titrated in the LTE, the investigator should decide whether it is clinically appropriate to transition these subjects to the optimal dose given the tolerability history and optimal dose selection (Investigators will be unblinded to treatment dose at this time). E.g., if a subject in the 10 mg dose group has to down titrate to one capsule (5 mg) then it is likely inappropriate to transition the subject to 70 mg if that is the chosen optimal dose for Phase 3 and LTE; however, this decision should be based on the Investigator's opinion. Down titration to one capsule BID after being switched to the optimal dose in the LTE will be permitted.

If a subject develops intolerable adverse events during the study, a down titration from two capsules to one capsule will be allowed. The Investigator should conduct an Unscheduled telephone or video visit with the subject to discuss and decide whether down titration to a lower dose is warranted. Careful consideration should be made whether to down titrate or not, and the decision to down titrate should be made when the alternative would be to withdraw study treatment due to drug intolerability. The Investigator should capture any adverse or clinical worsening events, and in cases where the Investigator agrees that down titration is appropriate, the CRO Medical Monitor should be notified as soon as possible. Subjects will not be allowed to up-titrate after having down titrated.

If it is determined by the Investigator that down titration is warranted, the subject will be instructed to take only 1 capsule BID from the assigned study drug bottles. The date and reason for down titration must be recorded in the subject's source documents and in the eCRF.

Down titration is also required if an ECG reveals, for a subject, a QTc interval that exceeds 500 msec, or a QTc progression of ≥ 60 msec (see [Section 5.9.2](#)).

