5.9.2 Prohibited Medicines

The following treatments are not permitted during the study:

- Inhaled prostacyclin therapies
- Warfarin (or any vitamin K antagonists), DOACs or dual antiplatelet therapy

Use of any of the above nonpermitted medicines and therapies require IMP discontinuation (see [Section 6.8](#)) (anti-platelet monotherapy with e.g. aspirin or clopidogrel is allowed).

The use of strong CYP3A4 inhibitors may increase the systemic exposure to imatinib. Likewise, strong CYP3A4 inducers may decrease the exposure of imatinib. It is unknown what contribution of systemically circulating AV-101 will contribute to potential efficacy or adverse events and so alternatives to strong CYP3A4 inhibitors or inducers should be considered.

High doses of oral imatinib are known to have the potential to prolong the QTc interval on the ECG. Drugs that are known to increase the QT interval should be used with caution. For a list of such drugs please refer to <https://crediblemeds.org>. In the event that a subject develops an absolute prolongation of the QTc interval to a value > 500 msec, or develops a change from baseline in the QTc interval of ≥ 60 msec, the subject should undergo a dose reduction. If a subject has already undergone a dose reduction for other reasons, then they should discontinue study drug. The subject should return for an unscheduled visit after two weeks of dose reduction and the ECG should be repeated. If there is a shortening of the QTc interval to < 500 msec, or the change from baseline is

now < 60 msec, the subject should remain on the reduced dose. If there is no change in the QTc interval after reducing the dose then the subject should be discontinued from study drug.

6 Study Assessments and Procedures

Before subjects commence any study-specific activities or procedures, including Week 24 assessments from AV-101-002 which will serve as baseline for this study, the Sponsor requires a copy of the study site's written Independent Ethics Committee/Institutional Review Board (IEC/IRB) approval of the protocol, informed consent form (ICF), and all other subject information and/or recruitment material, if applicable. Each subject must sign and date the ICF before participating in study-specific activities. If an unexpected circumstance occurs that would prohibit the subject from entering the study at Week 24 on AV-101-002, this may be discussed with the CRO Medical Monitor and/or Sponsor.

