8.3 Treatment Exposure, Estimated Number of Subjects in Group Comparisons of Interest

LTE-eligible subjects from the Phase 2b and Phase 3 parts of the parent study will complete 24-weeks of treatment as part of that study, additional weeks of treatment under the same active treatment arms as they enter LTE and until they start optimal dosing once this dose is identified at the end of Phase 2b.

LTE-eligible subjects from the Phase 2b and Intermediate Parts of the parent study who are randomized to placebo will be re-randomized in a blinded manner to any of the active treatment dose groups at LTE entry and prior to being treated with the optimal dose at the end of Phase 2b. Depending on the timing of their enrollment and initial treatment in the Intermediate part of the study, treatment duration under the parent study will be at least 24 weeks prior to being treated

with the optimal dose at the end of Phase 3. The actual duration of treatment during the parent study, during the waiting period for the optimal dose and during the LTE, will be reported.

LTE subjects will be treated at different dose levels prior to the optimal dose being identified. In addition, duration of treatment under the parent dose among those in the Phase 2b and Intermediate Parts may vary before the optimal dose is identified at the end of Phase 2b. Thus time-varying treatment exposure is a key characteristic of the combined parent and LTE trials and will be considered in describing levels and trends in safety and effectiveness endpoints recorded during the LTE trial.

The actual number of subjects by LTE treatment groups will be reported. Summary descriptive statistics will be reported for dose intensity and relative dose intensity by LTE treatment groups. Patterns of continuous dose intensity will be described by fitting a polynomial regression with dose intensity as a response variable and weeks in the study as polynomial splines. In addition, levels and patterns of dose intensity (and relative dose intensity) over LTE time intervals will be described.

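### Section 8.6 tabulates adverse events leading to withdrawal but not those leading to down titration or interruption, so the withdrawal table alone understates treatment-limiting intolerability

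*Combined protocol and SAP*

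**What the plan says.** Tolerability is part of what the study is for. Section 2.1 reads: "The objective of the study is to establish the long-term safety and tolerability of AV-101".

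Section 5.5 sets out what happens when a subject cannot tolerate the assigned dose: "If a subject develops intolerable adverse events during the study, a down titration from two capsules to one capsule will be allowed". It describes this as the step to take in place of stopping: "the decision to down titrate should be made when the alternative would be to withdraw study treatment due to drug intolerability". It also requires documentation: "The date and reason for down titration must be recorded in the subject's source documents and in the eCRF". Separately, Sections 5.5 and 5.9.2 call for a reduction after certain QTc findings ("the subject should undergo a dose reduction"). Section 7.7 provides for withholding drug after related Grade 3 events.

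On reporting, Section 8.6 lists its adverse event tables: "Tables of fatal adverse events, SAEs, treatment-related AEs, and adverse events leading to withdrawal from investigation product will be provided". Section 8.4 reports reasons for treatment discontinuation and study discontinuation. Down titration enters Section 8 only through exposure. Section 8.1 averages dose over weeks, allowing for titration, early stopping and missed doses together, and Section 8.3 adds: "Summary descriptive statistics will be reported for dose intensity and relative dose intensity by LTE treatment groups".

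**The concern.** A table of adverse events leading to withdrawal is normally where a reader looks to see how often a drug could not be tolerated. Here the protocol offers a half dose at the point where withdrawal for intolerability would otherwise follow. A subject who takes that route and stays on one capsule is not a withdrawal, so is absent from the table and from the Section 8.4 reasons. No other planned output shows, by reason, how many subjects lost the assigned dose because of an adverse event.

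This matters more than usual in this programme. Sections 1.1 and 1.2.3 record that oral imatinib was poorly tolerated and that its development in PAH was halted, and AV-101 is expected to do better. A withdrawal percentage quoted alone would answer that question only in part.

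**Working it through.** The plan states no rate of withdrawal or down titration, so there is no figure to reproduce. The check is mainly a comparison of sections.

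**1. Where each outcome would be reported**

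| Outcome for a subject with an adverse event | Event shown (8.6) | Link to loss of treatment shown | Reason shown |
|---|---|---|---|
| Permanent withdrawal | Yes | Yes, withdrawal table | Yes (8.4) |
| Down titration, stays on one capsule | Yes | No; only inside average dose intensity | No |
| Temporary interruption | Yes | No; only inside average dose intensity | No |

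The second row is the one that Section 5.5 ties to averted withdrawal.

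**2. Does dose intensity fill the gap?** Section 8.1's planned weekly doses reproduce: 10 × 2 × 7 = 140, 35 × 2 × 7 = 490 and 70 × 2 × 7 = 980 mg. One capsule halves each, so reductions do register. The reason does not. Assume that relative dose intensity means dose taken divided by the assigned two-capsule dose (the documents do not define it), and compare two groups:

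- Group A: 10% of subjects spend half of follow-up on one capsule and everyone else takes every dose. Mean = 1 − 0.10 × 0.5 × 0.5 = 0.975; median 1.
- Group B: every subject misses 2.5% of doses. Mean = 0.975.

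The means are equal. The spread differs: Group A has minimum 1 − 0.5 × 0.5 = 0.75 and SD 0.25 × √(0.10 × 0.90) = 0.075, while Group B has minimum 0.975 and SD 0. Section 8.1's standard descriptive statistics would show that some subjects in Group A took less drug. They would not show whether intolerance, a QTc finding, early stopping or missed doses was the cause.

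**3. How large could the understatement be?** Let w be the share of subjects withdrawn for adverse events and d the share down titrated for adverse events and kept on drug. The share of affected subjects missing from the withdrawal table is d/(w + d). All rates below are assumptions. N = 370 is the expected enrolment in Section 8.1.

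| w | d | In withdrawal table | Withdrawn or down titrated | Share missed |
|---|---|---|---|---|
| 10% | 5% | 37 | 56 | 5/15 = 33% |
| 10% | 10% | 37 | 74 | 10/20 = 50% |
| 10% | 20% | 37 | 111 | 20/30 = 67% |

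Over w = 5–15% and d = 5–20%, the share runs from 5/20 = 25% to 20/25 = 80%. It does not depend on N, so the maximum of 462 subjects gives the same percentages.

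**4. When should a combined count start?** Section 8.4 places baseline before the first dose in the parent study for Groups 1 and 2, and before the first LTE dose for Groups 3 and 4. Section 4.1 requires completion of the parent study, and Section 8.2 limits the safety set to subjects dosed in the LTE. Counted from first AV-101 dose, Groups 1 and 2 would have 24 weeks in which permanent withdrawal is impossible by construction; Groups 3 and 4 would not. That is immortal time, so the clock has to start at the first LTE dose.

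**The case against.** **The events are not lost.** A reader might infer that the withdrawal table is the plan's only tolerability output. It is not. Section 8.6 also plans treatment-emergent events by system organ class and preferred term, treatment-related events, severity, relationship to drug or inhaler, listings, and a negative binomial model for repeated events of special interest. An adverse event that prompts down titration appears there. What is missing is the classification by action taken. This stands, and it limits the point.

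**Dose intensity reveals reductions.** A reader might also infer that a group with many down titrations would look as well tolerated as a group with none. That could be true of the withdrawal table read alone, but not of the whole plan, because dose intensity is summarised by group and over time and its spread would differ. What it lacks is the reason.

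**Not every down titration is an averted withdrawal.** Section 5.5 words the criterion as guidance, and QTc-driven reductions arise from a separate rule. This stands: they need their own line. Section 7.1.1 also restricts when an ECG finding is reported as an adverse event, so a table built only from adverse events could omit some of them.

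**Detail is deferred.** Section 8 calls itself an overview and leaves details to a SAP, and a table by action taken could be added there. The gap can be closed that way, but nothing in the documents does so. Section 8.6 does specify one table by action taken, and it covers withdrawal alone.

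**Conclusion.** The point holds in a limited form. Section 5.5 directs some treatment-limiting intolerability to down titration, while Sections 8.6 and 8.4 report only withdrawal by cause. Read alone, the withdrawal table will therefore understate how many subjects could not stay on the assigned dose because of adverse events. The table would be correct for what it measures; it measures only part of what the tolerability objective needs.

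The size is unknown. The 25% to 80% range rests wholly on assumed rates and shows only that the gap could be material. A reader might want to state that the reported figure is low by some definite factor. The documents give no withdrawal or down-titration rates, so no such factor is supported. Entrants must also have finished the parent study without a toxicity that led to stopping drug (Section 4.1), which makes rates from elsewhere hard to carry over.

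The conclusion assumes that investigators follow the Section 5.5 guidance and that no SAP text outside the documents already adds these tables. It is a reporting point and takes no view on the dosing rules.

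**What to change.** Add to Section 8.6, and carry into the SAP:

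1. Tables of adverse events leading to down titration and, separately, to temporary interruption, by LTE group, treatment interval and dose at onset. Include the number and percentage of subjects down titrated by reason, with QTc-driven reductions shown separately.
2. Next to the withdrawal table, a combined count of subjects with AE-driven down titration or permanent withdrawal during the LTE, each subject counted once. If this is shown as cumulative incidence, start at the first LTE dose for all groups. Add a note that Groups 1 and 2 remain selected for having tolerated 24 weeks of active drug in the parent study.

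No new data collection should be needed. Section 5.5 puts the date and reason of down titration in the eCRF, and Section 7.5 has each adverse event report record the action taken, including dose modification. The sponsor should confirm that interruption is coded as its own category. The cost is a change of wording, some extra programming and, probably, a less favourable tolerability figure.
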